8.5 Hydroxychloroquine Dose Reduction

Any Adverse Event Grade 3 or higher requires HCQ to be withheld. Treatment may be resumed once toxicity is \leq Grade 2 according to the below Dose Reduction Schema (Table 1). If toxicity does not resolve or improve to \leq Grade 2 within 7 days, participant will be withdrawn from active treatment unless granted an exception by the Medical Monitor. Medical Monitor should be notified of all toxicities requiring dose withholding or dose adjustments via email or phone.

Any AE = Grade 2 and **attributed as possibly, probably or definitely related to HCQ** will result in a dose reduction of HCQ as described in Table 1.

If AE remains = Grade 2 following the first dose reduction **and attributed as possibly, probably or definitely related to HCQ** following the second dose reduction, then the participant should discontinue treatment.

No more than 2 dose reductions are allowed. It is recommended that dose reductions occur at a minimum of 48 hours apart.

Table 1: Dose Reduction Schema

Sub-Study	Dose mg/day	First dose reduction	Second Dose reduction
1 (PATCH 2)	400 mg (two tablets) twice daily	400mg (two tablets) once daily	200 mg (one tablet) once daily
2 (PATCH 3)	600 (three tablets) mg daily	400 mg (two tablets) once daily	200 mg (one tablet) once daily

Reported non-serious toxicities attributable to HCQ include nausea, anorexia, vomiting, constipation, diarrhea and rash. For any of these AEs occurring at Grade < 2 , HCQ may be continued and the AE managed with supportive care. For **Any AE** with a Grade ≥ 3 , HCQ will be held until the toxicity improves to \leq Grade 2, after which HCQ may be restarted at a reduced dose as described in Table 1.

Example: Management of diarrhea in randomized subjects

Grade 1: (an increase in stool up to 3 per day) results in no change to HCQ

Grade 2: (an increase in stool up to 4-6 per day) results in a Dose Reduction according to Table 1

Grade 3+: (an increase in stool up to 7 or more per day) results in Withholding of HCQ until AE at Grade level 2 or less, followed by a reduction in dose per Table 1.

9.0 ADVERSE EVENTS AND REPORTING

The timely reporting of adverse events (including toxic deaths) is required by the Food and Drug Administration. The reporting of toxicities is part of the data reporting for this study. The investigator is responsible for ensuring that all adverse events (AEs) and serious adverse events (SAEs) as self-reported during the study are collected and reported to the FDA, appropriate IRB(s), in accordance with CFR 312.32 (IND Safety Reports).

9.1 Adverse Events Definition

An **adverse event** (AE) is any symptom, sign, illness or experience that develops or worsens in severity during the study that does not necessarily have a causal relationship with this treatment. Intercurrent illnesses or injuries should be regarded as adverse events. Abnormal results of diagnostic procedures are considered to be adverse events if the abnormality:

- results in study withdrawal
- is associated with a serious adverse event
- is associated with clinical signs or symptoms
- leads to additional treatment or to further diagnostic tests or considered by the investigator to be of clinical significance

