PATCH 3 Inclusion (Sub-Study 2): Currently employed as a health care worker ([name]; Doctor of Osteopathic Medicine, DO; Nurse Practitioner, NP; Physician's Assistant, PA; and [name] or other members of the medical care team with significant COVID-19 exposure); asymptomatic and presumed negative for COVID-19 (no confirmatory testing conducted); scheduled for an average of ≥ 20 hours per week of clinical care over the next two months (or equivalent indicating at least part-time employment). Participant will be asked to comply with their employer's potential or confirmed COVID-19 incident protocol and must agree to undergo COVID-19 testing per standard of care using an FDA approved method upon the presentation of symptoms indicative of an influenza like illness; if a confirmatory COVID-19 diagnosis is given, participant will be offered to cross-over to HCQ 600 mg qd for 14 days. At the end of the 60-day medication period, participants remaining undiagnosed for COVID-19 will undergo virus and serology testing. (See Appendix- PATCH3 process flows)

PATCH 2 & PATCH 3 Combined Exclusion Criteria

(See Study Exclusions and Content Job Aid)

- Allergy to hydroxychloroquine, 4 aminoquinolines, or quinine
- Known G6PD deficiency
- Pregnant or lactating or intention of becoming pregnant during the study as self-reported during enrollment screening
- Receiving any trial treatment drug for 2019-nCoV within 14 days prior to screening evaluation (off label, compassionate use or trial related)
- Known retinal disease including but not limited to macular degeneration, retinal vein occlusion, visual field defect, diabetic retinopathy
- History of interstitial lung disease severe emphysema or asthma, or chronic pneumonitis Current diagnosis of porphyria or psoriasis
- Serious intercurrent illness that requires active intravenous therapy, intense monitoring, or frequent dose adjustments for medication including but not limited to infectious disease, cancer, autoimmune disease, cardiovascular disease

PATCH 2 & 3 TRIAL

- Have undergone major abdominal, thoracic, spine or CNS surgery in the last two months, or plan to undergo surgery during study participation
- Is receiving cytochrome P450 enzyme-inducing anticonvulsant drugs (i.e. phenytoin, carbamazepine, Phenobarbital, primidone or oxcarbazepine) within four weeks of the start of the study treatment
- Currently taking digoxin
- History or evidence of increased cardiovascular risk including any of the following:

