COVID-19/SARS-CoV-2 testing: Upon the presentation of symptoms indicative of an influenza like illness, participants will be asked to undergo testing for SARS-CoV-2 virus. Participants undiagnosed for COVID-19 at Day 60 will also be tested for SARS-CoV-2 and IgM/IgG antibodies (via serology testing) on either Day 61, 62, or 63.

Clinical Symptom monitoring: The study team will assess AEs, symptoms, and record temperature (either reported temperature or self-report of fever) for any participants taking active medication (placebo or HCQ). Worsening COVID symptoms and/or new or worsening AE's will be reviewed by the PI's for causality to study drug. The rate of conversion to receiving a positive COVID-19 test result in each arm at the 2-month mark will be used to assess the primary endpoint.

Pill count and Journal: Participants will be contacted to compare data entry on the portal and collect any missed entries over the phone.

Participants will be instructed to call 911 upon immediate presentation of the following symptoms as identified by the CDC as requiring emergency action: bluish lips or face; new confusion/dizziness or inability to arouse; persistent pain or pressure in the chest (not caused by coughing); and difficulty breathing (including severe shortness of breath and single word speech).

Participant confidentiality is strictly held in trust by all personnel granted access to the trial data. Therefore, the study data, and all other information generated will be held in strict confidence. No information concerning the study, or the data will be released to unauthorized parties.

The study investigators and study team, the research sponsor and its designees, personnel from ProHealth with authorized access to study data, government agencies, reviewing Institutional Review Board (IRB), regulatory agencies and/or company supplying study product may inspect all documents and records required to be maintained by the sponsor, including but not limited to, clinical, pharmacy and lab records for participants enrolled in the study. All applicable parties will permit access to such records.

The participant's study contact information will be securely stored within the online study portal for internal use during the study. At the end of the study, all records will continue to be kept in a secure location for as long as dictated by the reviewing IRB and institutional policies.

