9.2 Adverse Events Reporting Period

The study period during which adverse events must be reported is defined as the period from the initiation of the first study treatment to the last administration of study treatment.

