10.2 Hospitalization, Prolonged Hospitalization or Surgery

Any adverse event that results in hospitalization or prolonged hospitalization should be documented and reported as a serious adverse event unless specifically instructed otherwise in this protocol. Any condition responsible for surgery should be documented as an adverse event if the condition meets the criteria for an adverse event.

Neither the condition, hospitalization, prolonged hospitalization, nor surgery are reported as an adverse event in the following circumstances:

- Hospitalization or prolonged hospitalization for diagnostic or elective surgical procedures for a preexisting condition. Surgery should not be reported as an outcome of an adverse event if the purpose of the surgery was elective or diagnostic and the outcome was uneventful.
- Hospitalization or prolonged hospitalization required to allow efficacy measurement for the study.
- Hospitalization or prolonged hospitalization for therapy of the target disease of the study, unless it is a worsening or increase in frequency of hospital admissions as judged by the clinical investigator.

Expected adverse events are those adverse events that are listed or characterized in the Package Insert or current Investigator Brochure.

Unexpected adverse events are those not listed in the Package Insert (P.I.) or current Investigator Brochure (I.B.) or not identified. This includes adverse events for which the specificity or severity is not consistent with the description in the P.I. or I.B. For example, under this definition, hepatic necrosis would be unexpected if the P.I. or I.B. only referred to elevated hepatic enzymes or hepatitis.

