PATCH 2 (Sub-Study 1): Rate of secondary infection of housemates is a binomial count by household. We will summarize the proportion or rate by group, with 95% CI. With sufficient data, we will explore subgroups, patient, and secondary patient characteristics using logistic regression. Rate of hospitalization is a binary measure. We will summarize rates by group and estimate the odds-ratio for treatment. Adverse event rates will be summarized as a count by participant, and mean count by group, and we will estimate a rate-ratio for treatment. We will summarize rates by group and estimate the odds-ratio for treatment.

PATCH 3 (Sub-Study 2): Rate of hospitalization is a binary measure. We will summarize rates by group and estimate the odds-ratio for treatment. Adverse event rates will be summarized as a count by participant, and mean count by group, and we will estimate a rate-ratio for treatment. We will summarize the count of shifts missed by group and estimate the rate ratio for treatment.

REFERENCES

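### Read literally, PATCH 3's adverse-event rate ratio counts symptomatic COVID-19 as harm, so efficacy can pull it towards or below 1; sections 9.1 and 10.2 are not reconciled

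*Combined protocol and SAP*

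**What the plan says.** Section 9.1 defines an AE as "any symptom, sign, illness or experience that develops or worsens in severity during the study", whether or not the drug caused it, and adds: "Intercurrent illnesses or injuries should be regarded as adverse events". COVID-19 is not excepted. Section 3.1 admits health care workers to PATCH 3 only if they are free of symptoms and presumed negative, so symptomatic COVID-19 during dosing is a new illness. Section 9.2 sets the AE window as "the period from the initiation of the first study treatment to the last administration of study treatment".

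For PATCH 3, section 16.2 says: "Adverse event rates will be summarized as a count by participant, and mean count by group, and we will estimate a rate-ratio for treatment". It neither sets COVID-19 apart nor splits by relatedness, although section 9.4.1 collects relatedness. AE rate is a named secondary objective (section 1.2). Because 16.2 reports no significance tests for secondary outcomes, the estimate and its interval are the whole read-out.

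Section 10.2 points the other way for admitted cases: "Neither the condition, hospitalization, prolonged hospitalization, nor surgery are reported as an adverse event in the following circumstances", and one listed circumstance is "Hospitalization or prolonged hospitalization for therapy of the target disease of the study", unless the investigator judges it a worsening or an increase in admissions. The target disease is not defined for PATCH 3. Section 8.4 says "Worsening COVID symptoms and/or new or worsening AE's will be reviewed by the PI's for causality to study drug": it names the two side by side, gives both the same review, and does not say which enter the count.

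Sections 9.4 and 9.6 ask for signs and symptoms to be recorded under one diagnosis where it is known. Under sections 4.0 and 5.0, a confirmed COVID-19 diagnosis unblinds the participant. Placebo participants are then offered 14 days of HCQ and keep logging symptoms and AEs while taking it.

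**The concern.** Symptomatic infection is part of what PATCH 3 hopes to prevent. If those same illnesses also sit in the safety count, an effective drug improves its own harm estimate, and a real excess of drug-related events shows as a smaller one. This matters because healthy workers take HCQ for up to 60 days, and AE burden is the main counterweight to any benefit.

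The open point between 9.1 and 10.2 adds a second problem. COVID-19 managed at home is an AE under 9.1, while an admitted case may not be one under 10.2. Two analysts following the document could report different ratios from the same records.

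**Working it through.** **No AE figure of the plan's own to reproduce.** The documents give no AE rate by arm and no expected AE ratio. The side-effect guide in Appendix 4 gives frequency bands for people on HCQ (nausea, stomach pain and cramps in 10% or more), not a mean count per participant.

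**Inputs from section 16.1.** 175 per arm; infection rates of 10% (placebo) and 1% (HCQ). Expected infections: 175 × 0.10 = 17.5 and 175 × 0.01 = 1.75, a difference of 0.09 per participant.

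**Assumed inputs.** b = mean non-COVID AEs per placebo participant; R = true HCQ/placebo ratio for those AEs; k = AE entries per infection. Sections 9.4 and 9.6 point to k of about 1, which is the main case; k = 3 and 5 are sensitivity cases.

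**Formulas.**

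- HCQ effective as planned: reported ratio = (bR + 0.01k) / (b + 0.10k).
- No efficacy, 10% in both arms: reported ratio = (bR + 0.10k) / (b + 0.10k).

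Example, b = 0.6, R = 1.5, k = 1: (0.90 + 0.01) / (0.60 + 0.10) = 0.91 / 0.70 = 1.30.

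**Main case, k = 1**

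| b | R = 1.5, effective | R = 2.0, effective | R = 1.5, no efficacy |
|---|---|---|---|
| 0.2 | 1.03 | 1.37 | 1.33 |
| 0.3 | 1.15 | 1.525 | 1.375 |
| 0.6 | 1.30 | 1.73 | 1.43 |
| 1.0 | 1.37 | 1.83 | 1.45 |

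With no toxicity at all (R = 1.0, HCQ effective), the reported ratio is 0.70 at b = 0.2 and 0.96 at b = 2, so HCQ would look somewhat safer than placebo.

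**When the ratio falls below 1.** This happens when bR + 0.01k < b + 0.10k, that is, when b < 0.09k / (R − 1).

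| k | R = 1.5: b below | R = 2.0: b below |
|---|---|---|
| 1 | 0.18 | 0.09 |
| 3 | 0.54 | 0.27 |
| 5 | 0.90 | 0.45 |

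For instance, with k = 3 and R = 1.5 the reported ratio is 0.80, 1.03 and 1.18 at b = 0.3, 0.6 and 1.0.

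**Why 0.09 per participant is an upper bound under the plan's scenario.** The 10% and 1% belong to the primary endpoint. Infections found only by testing on Day 61 to 63 fall after the 9.2 window. Positives without symptoms are AEs only if they meet another 9.1 condition. Section 10.2 may remove admitted cases.

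**Crossover.** If AEs logged by placebo participants on crossover HCQ stay in the placebo count, they push the ratio in the same direction. Section 16.2 gives no rule, and this effect is not in the tables.

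**The case against.** Four stronger readings are tempting, and the documents do not support them.

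- A reader might infer that the plan states that infections are in the AE count. It does not. Inclusion is what 9.1 and 16.2 give when followed literally, and 10.2 limits it.
- A reader might take 8.4 as a second definition of an AE. It only names COVID symptoms beside AEs and sends both to the same causality review.
- A reader might infer that HCQ toxicity would be hidden or reversed. For true ratios of 1.5 to 2.0, that needs several entries per infection, against the direction of 9.4 and 9.6, or very low background counts. With one entry per infection and b of 1 or more, a true 1.5 still shows as at least 1.37.
- A reader might treat 17.5 versus 1.75 as the number of COVID-19 AEs. It is a ceiling.

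It is also fair to say that the ratio is descriptive, that no decision rule uses it, that relatedness and grade are collected, and that day-to-day safety rests on review of individual events and an independent medical monitor. An all-cause count is a legitimate measure of total burden. If HCQ does nothing, the effect is dilution of the kind any unrelated illness causes.

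These points limit the size of the problem but do not remove it. Section 16.2 plans no table by relatedness. Because diagnosis unblinds, later causality calls can be made with the arm known. One entry per infection is not assured either: 9.6 applies where the diagnosis is known at reporting, and PATCH 3 relies on daily self-report that can precede a test result.

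**Conclusion.** The point holds in a limited form. The literal text puts symptomatic COVID-19 arising during dosing into PATCH 3's AE ratio, 10.2 takes out some admitted cases, and no section settles which applies. If HCQ works as planned, the harm ratio is pulled towards or below 1 by efficacy. At one AE per infection the likely form is attenuation: an assumed true 1.5 shows as about 1.15 to 1.37, and an assumed 2.0 as about 1.52 to 1.83, for placebo means of 0.3 to 1.0. Without efficacy, 1.5 becomes 1.33 to 1.45 for means of 0.2 to 1.

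These sizes rest on the plan's infection rates as an upper bound and on assumed values of b, R and k. The primary comparison and the stopping boundaries are not affected. The change is worth making because it is cheap and because the harm estimate should not improve merely through efficacy.

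**What to change.** In section 16.2, for PATCH 3:

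1. Report the AE rate ratio excluding COVID-19 and its signs and symptoms, beside the all-event ratio.
2. Set the exclusion flag by a prespecified rule applied without regard to arm: a test-confirmed case, a listed set of symptoms, and a fixed date window around the positive test. Case-by-case attribution would not do, because diagnosis triggers unblinding.
3. Show AEs after crossover to HCQ separately, and do not count them as placebo-arm AEs in this comparison.

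Then reconcile 9.1 with 10.2 on whether COVID-19 is recorded as an AE, and define the target disease for PATCH 3.

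The cost is a rule-based flag on the AE record, a crossover marker, and a few table rows. Some symptoms will be misclassified, which is why the total is reported as well. The rule governs classification only: entries made after diagnosis still come from participants who know their arm.

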9.2 Adverse Events Reporting Period

The study period during which adverse events must be reported is defined as the period from the initiation of the first study treatment to the last administration of study treatment.

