2.4 Low dose versus high dose HCQ

In HCQ studies in cancer patients we conducted population pharmacokinetic studies and pharmacodynamic studies and determined that 800-1200 mg daily was required to effectively and consistently impair the lysosome in peripheral blood mononuclear cells. Our PK studies determined that it took roughly 2 weeks to achieve steady state in cancer patients. For these reasons there is rationale to propose a high dose (600 mg po bid) prolonged schedule treatment (2 weeks). In contrast an in vitro study recently published which included PK-PD modeling extrapolated from published PK studies indicated that HCQ was very active against COVID-19 but only 400 mg po bid X1 followed by 200 mg po bid for 5-10 days was enough for treatment. A recent non-randomized open label French trial Geuret et al Int J Antimicrobial Agents 2020) showed that 600 mg qd of HCQ cleared virus in 70 % of mildly ill hospitalized patients compared to 12.5% at 6 days of control patients. This generates a major question in how to use this agent in different populations that can best be answered in this two-part placebo controlled randomized trial.

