9. Three times a week, participants will be called by clinical research coordinators to assess AEs and symptoms with all discussions well-documented. Clinical research coordinators may clinically escalate any medical determinations to Co-PI
10. After Day 14, which marks the end of the treatment period, participants will no longer be expected to continue self-reporting information into the study portal. Participant will undergo follow-up testing for COVID-19 at two additional time points. The first will be either day 15, 16 or 17, with the second on either on day 29, 30 or 31
11. If during active participation, the participant reports worsening of symptoms related to COVID-19 from baseline, this is reported to the PI for further clinical evaluation

Participant Procedure PATCH 3 (Sub-Study 2) (See study process flows)

1. Interested participants self-refer for study by completing online eligibility checklist on study portal (www.patchstudy.com)
2. Review inclusion and exclusion criteria:
 - Currently employed as a health care worker ([name]; Doctor of Osteopathic Medicine, DO; Nurse Practitioner, NP; Physician's Assistant, PA; and [name] or other members of the medical care team with significant COVID-19 exposure);
 - Asymptomatic and presumed negative for COVID-19 (no confirmatory testing conducted);
 - Scheduled for an average of >20 hours per week of clinical care over the next two months (or equivalent indicating at least part-time employment).
 - Willing to comply with their employer's potential or confirmed COVID-19 incident protocol
 - Agrees to undergo COVID-19 testing per standard of care using an FDA approved method upon the presentation of symptoms indicative of an influenza like illness (if a confirmatory COVID-19 diagnosis is given, participant will be offered to cross-over to HCQ 600 mg qd for 14 days.)
3. Reviews the study and the Informed Consent Form with the subject and obtains informed consent via DocuSign
4. Participant study ID is assigned, and subsequently, randomized into a study arm (HCQ or placebo).

PATCH 2 & 3 TRIAL

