3. Immunosuppressive medications, including, corticosteroids at doses exceeding 10mg/day of prednisone or equivalent, methotrexate, azathioprine, and TNF-alpha blockers. Use of immunosuppressive medication for the management of study treatment-related AEs or in subjects with contrast allergies is acceptable. In addition, use of topical, inhaled and intranasal corticosteroids is permitted
4. Live attenuated vaccines during the study through 180 days after the last dose of both drugs

7.3 Duration of Protocol Treatment and Follow-up.

PATCH 2 (Sub-Study 1) duration of treatment is 14 days (two weeks) with follow-up with COVID-19 testing on Day 15, 16 or 17, and Day 29, 30 or 31 where Day 1 marks the first day blinded study drug is taken by the participant.

PATCH 3 (Sub-Study 2) duration of treatment is up to 60 days with an option to cross-over for participants taking placebo upon presentation of symptoms indicative of an influenza like illness and testing positive for COVID-19 (or a COVID-19 diagnosis is made by a health care provider). Participants remaining undiagnosed for COVID-19 by Day 60 will undergo testing for SARS-CoV-2 and IgM/IgG antibodies on either Day 61, 62, or 63. The maximum study medication duration and follow-up testing is 63 days.

7.4 Crossover from Control to HCQ arm.

PATCH 2 (Sub-Study 1): There is no cross-over.

PATCH 3 (Sub-Study 2): Participants that develop symptoms indicative of an influenza like illness and diagnosed with COVID-19 will be unblinded. If they were assigned to the placebo arm and deemed appropriate, they will be offered the option crossover to HCQ 600 mg qd for 14 days.

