10.3 Deaths

All deaths that occur during the protocol-specified AE reporting period (see Section 12.1), regardless of attribution, will be reported to the appropriate parties. When recording a death, the event or condition that caused or contributed to the fatal outcome should be reported as the single medical concept. If the cause of death is unknown and cannot be ascertained at the time of reporting, report "Unexplained Death".

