15.0 MEASUREMENT OF EFFECT

15.1 Definitions

Evaluable for toxicity: All participants will be evaluable for toxicity from the time of their first treatment with HCQ or placebo through final assessment.

Evaluable for primary outcome: Participants who received at least one continuous week of HCQ will be evaluable for the primary outcome.

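### Mandatory AE reporting ends at the last dose, toxicity is evaluable through final assessment, and the AE rate ratio names neither a window nor an exposure offset

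*Combined protocol and SAP*

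**What the plan says.** AE rate is a secondary objective in both sub-studies (Section 1.2). Three sections bear on the period it covers.

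- Section 9.2 sets the mandatory AE reporting period: "from the initiation of the first study treatment to the last administration of study treatment".
- Section 15.1 sets a longer one: "All participants will be evaluable for toxicity from the time of their first treatment with HCQ or placebo through final assessment".
- Section 16.2 summarises AEs as a count per participant and a mean count by group, with a rate ratio for treatment. It names no period and no adjustment for time observed.

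Section 7.3 gives the dates. PATCH 2 has 14 days of treatment, then "follow-up with COVID-19 testing on Day 15, 16 or 17, and Day 29, 30 or 31". PATCH 3 has up to 60 days of treatment and testing on Day 61-63: "The maximum study medication duration and follow-up testing is 63 days".

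Routine capture mostly follows the shorter period. After Day 14, PATCH 2 "participants will no longer be expected to continue self-reporting information into the study portal" (Section 4.0). In PATCH 3, Section 4.0 asks for AE entries on days when study tablets are taken, and Section 8.4 has staff assess AEs in participants who are taking them.

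For deaths, Section 10.3 covers "All deaths that occur during the protocol-specified AE reporting period" and refers the reader to Section 12.1 for that period. Section 12.0 has no subsections.

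**The concern.** Under 9.2 the reporting period closes whenever a participant stops drug. Its length then depends on treatment experience after randomization. Section 8.5 takes participants off active treatment when toxicity does not improve within 7 days, and Section 12.0 lists the same situation, and toxicity persisting after two dose reductions, among reasons for leaving the study. Someone who stops for toxicity therefore has a shorter mandatory reporting period than someone who tolerates the tablets.

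A comparison of raw counts assumes that both arms were watched for the same time. If the active arm stops earlier for toxicity, its later non-serious events need not be reported and its mean count is too low. The AE rate ratio then understates the difference that the outcome is meant to describe. Because 9.2 and 15.1 disagree and 16.2 is silent, two analysts could follow the plan faithfully and count different events.

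**Working it through.** The plan states no AE rate, AE window or AE power, so there is no figure to reproduce. The check compares the two periods and counts days.

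**Inputs.** Dosing lasts 14 days in PATCH 2 and up to 60 in PATCH 3; the last scheduled tests are on Day 29-31 and Day 61-63 (Section 7.3). Section 15.1 does not define final assessment; reading it as the last scheduled test is an assumption.

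**Formulas.** Share covered by 9.2 = day of last dose / day of final assessment. Days left out = day of final assessment − day of last dose.

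| Case | Share covered | Days left out |
|---|---|---|
| PATCH 2, full course | 14/31 to 14/29 = 45% to 48% | 15 to 17 |
| PATCH 3, full course | 60/63 to 60/61 = 95% to 98% | 1 to 3 |
| PATCH 2, last dose Day 7 (assumed) | 7/31 to 7/29 = 23% to 24% | 22 to 24 |
| PATCH 3, last dose Day 7 (assumed) | 7/63 to 7/61 = 11% | 54 to 56 |

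**Who stops early.** In PATCH 2, anyone whose enrolment test is negative is told to stop (Section 4.0). Section 16.1 expects 100 positives among 500 enrolled, so about 500 − 100 = 400 would stop on their result. That shortens their 9.2 period, but the cause is the enrolment test and not evidently the assigned arm. Stopping for toxicity is the route by which the arms could differ.

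**Direction of the effect.** Suppose, for illustration only, that AEs occur at a constant rate within each arm, that those who stop do so halfway through dosing, and that fractions f_H (HCQ) and f_P (placebo) stop. Relative to a count over the whole dosing period, the ratio of mean counts is multiplied by

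(1 − f_H/2) / (1 − f_P/2).

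- f_H = 0.10, f_P = 0.10: 0.95/0.95 = 1.00
- f_H = 0.20, f_P = 0.05: 0.90/0.975 = 0.92
- f_H = 0.30, f_P = 0: 0.85/1 = 0.85

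None of these inputs is in the documents. The sums show the direction when HCQ stops more often, and no effect when stopping is equal. They do not estimate the bias.

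**What is collected after the last dose.** Section 10.0 collects all serious AEs from consent, related or not, and fatal events are serious by its definition. It then limits later reporting to related events after time periods that it never states. Section 9.3 follows unresolved AEs and asks participants to report later events thought related. Section 9.4 assesses AEs at each contact and records possibly related serious events after the study period. What has no mandate is a new, non-serious AE that begins after the last dose.

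**The case against.** The strongest reply is that 9.2 governs reporting and 15.1 governs evaluation, and that no text applies the 9.2 period to the AE outcome. A reader might infer that events after the last dose go uncounted. The documents do not support that: 16.2 leaves the period open, and 9.3, 9.4 and 10.0 all reach past dosing. Nor do they support calling the last 17 of 31 PATCH 2 days (55%) uncollected. The three-times-weekly coordinator calls have no stated end at Day 14; only portal entry does. These points stand, and they limit the gap to new non-serious events.

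A reader might also infer that deaths after the last dose are missed. Fatal events are serious events collected from consent, and Section 11.0 separately requires expedited reporting of unexpected, related deaths within 30 days of drug. The defect in 10.3 is its broken reference.

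Section 2.4 says "Our PK studies determined that it took roughly 2 weeks to achieve steady state in cancer patients", which might suggest that toxicity appears just as the PATCH 2 period closes. Time to steady state does not show that events begin after dosing ends, and the documents give no data on delayed events.

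Finally, the toxicity that causes stopping arises on drug and is reportable, and AE results are descriptive, without significance tests. Both are true. Neither protects the comparison of counts, because other events in people who stopped are still cut off. Volunteered reports of events thought related do not replace uniform collection.

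**Conclusion.** The concern holds in a limited form. Sections 9.2 and 15.1 contradict each other, and 16.2 does not say which period defines the count. New non-serious AEs after the last dose fall outside mandatory reporting for 15-17 days in a PATCH 2 completer and 1-3 days in a PATCH 3 completer. In PATCH 3 the issue is therefore almost entirely about early stoppers.

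A downward pull on the rate ratio is conditional: it needs earlier stopping for toxicity in the active arm and an analysis confined to events reported under 9.2. Its size cannot be derived from the documents. The day counts rest on reading final assessment as the last scheduled test. The primary outcomes, sample size and power are unaffected. The change should be made because it protects a stated secondary outcome in both sub-studies at little cost.

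**What to change.** - In 9.2, 10.3 and 15.1, state one AE window for everyone who took a dose, whether or not drug was stopped: first dose through the final scheduled assessment (Day 31 in PATCH 2, Day 63 in PATCH 3), or the end of a crossover course if later. The last clause matters because a 14-day course starting on Day d ends on Day d + 13, which is past Day 63 for any start after Day 50. Keep collection of serious events from consent.
- Replace the reference to Section 12.1 in 10.3 with the section that holds the window.
- State in 4.0, 8.4 and 12.0 that stopping tablets does not end AE follow-up unless consent is withdrawn.
- In 16.2, count AEs over that window, with a log person-time offset for incomplete follow-up. Report post-crossover events in PATCH 3 separately, since they occur on HCQ in people randomized to placebo. An on-treatment rate can stay as a supporting summary.

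The cost is protocol wording, a scripted AE question at test contacts already planned, and a brief contact for early stoppers who would not otherwise be seen. No dosing or clinical rule changes.
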